Unique Protocol ID: JCHP-2

Brief Title: Omega-3 Supplementation to Both Parent and Adolescent

Official Title: Omega-3 Supplementation to Both Parent and Adolescent to Reduce Behavior Problems

Document Date: May 16, 2018

Experimental Design and Methods

This section provides the design and method of the overarching study within which the three aims will be tested. We also briefly specify further programmatic goals of this line of study, and also how the specific expertise of the research team will help ensure feasibility. As with the pilot study, methodology and ultimately reporting of results will follow CONSORT 2010 guidelines (Moher et al., 2010).

Design Overview

The study design will consist of a stratified, double-blind, placebo-controlled, factorial, randomized controlled trial of children and their caregivers in a community sample in Mauritius. This closely follows the design of the pilot study (Raine et al. 2015). Unlike the pilot study however, it will utilize a 2x2 factorial design, in which children *and* their parents will be randomly assigned to either omega-3 supplementation (treatment condition) or a placebo (control condition), and will have an extended follow-up at 18 months. This results in 4 groups: (1) child and caregiver both receiving omega-3, (2) child receives omega-3, caregiver receives placebo, (3) caregiver receives omega-3, child receives placebo, (4) both parent and child receive placebo. Assessments will take place at 0 months (baseline), 6 months (end of supplementation), 12 months (6 months post-treatment), and 18 months (12 months post-treatment).

Background To The Sample and the Mauritius Child Health Project

Adolescents and caregivers will be drawn from the Mauritius Child Health Study, a multi-generational study involving three generations of subjects. Details of these three generations are provided in a cohort profile (Raine et al. 2010). Originally set up by [name] (Consultant), this longitudinal study covers early child health and development and the identification of early risk factors (including nutrition) for later psychopathology, as well as early primary prevention. Early factors that shape later cognitive functioning have also been a focus. Given the pilot findings and longitudinal data on the parents, it provides a unique platform on which to build.

Participants, Potential Attrition, and Strategies to Deal with Attrition

Participants will consist of 400 pairs of children and their caregivers (total N = 800). This replicates cell sizes in the pilot data and allows close comparability, with 100 children and 100 adults in each of four cells. The caregivers consist of the second generation participants (their parents are the first generation) who originally comprised the birth cohort. Their adolescent children are the third generation. All caregivers have previously participated in the Mauritius Child Health Project (Raine et al., 2010). Adolescents will be aged between 11 and 18 years old, willing to participate in an RCT, and residing in the community. Exclusion criteria consist of: (1) allergy to fish or fish products, (2) use of fish oil supplementation in the past six months, (3) intellectual disability, (4) participation in the prior RCT. There are currently 1,126 children aged 11-18 years actively participating in the Mauritius Child Health Project (51.2% female; 73.2% Indian, 24.5% Creole, 2.3% other), 124 of whom took part in the prior RCT and will be excluded. Written informed consent will be obtained from the parents with assent obtained from adolescents. The study will take place in interview rooms at the project headquarters in Quatre Bornes.

Attrition is an issue in all RCTs. In our pilot data however, attrition was only 8%, even after one year, and is likely attributable both to the long-standing intergenerational relationships between our research team in Mauritius and the participants. Attrition may nevertheless be slightly more with the longer follow-up. We have three strategies to deal with attrition. First, analyses will be intention-to-treat, including all participants regardless of drop-outs. Second, we will enhance participation using staggered incentives for completion. Third, we will code for missingness and assess whether it moderates treatment outcome.

Randomization

Participants will be randomized into four groups using urn randomization, a covariate adaptive randomization method (Wei & Lachin, 1988). Adaptive randomization is employed because it protects the study from bias while promoting study objectives, it improves power over standard designs, and it balances assignment of treatment across covariates in a way superior to traditional stratification (Rosenberger et al., 2012). We aim to achieve balanced groups on three main child covariates: age, gender, and ethnicity. An advantage of the Mauritius cohort is that we have data on the parents' externalizing behavior over the life-course (Raine et al. 2010) which we could add as a fourth covariate to further ensure that groups are balanced.

Omega-3 Intervention

Omega-3 supplementation. As in the pilot study, this consists of a 200 ml drink. The base drink in both treatment and placebo conditions consists of fruit juice containing vitamin D (0.85 micrograms) and antioxidants (ferric reducing ability of plasma value of 0.71 mmol/100g). For the treatment condition only, 1660 mg of omega-3 (550 mg of DHA, 550 mg of EPA, 560 mg of alpha-linolenic acid) is added to the base drink. Placebo drinks are matched exactly with the fish-oil drink in terms of size, appearance, and flavor. Caregiver and child drinks are differentially color-coded.

This drink is chosen because: (i) it contains a higher dosage of omega-3 than standard capsules in a small liquid quantity (60.6% of a standard can of cola) suitable for child / adolescent consumption, (ii) the fruit-flavored drink may be better tolerated and result in higher compliance with children than fish-oil capsules.

Treatment duration and administration. As in the pilot study, treatment duration will be six months. It was chosen because prior studies have usually been 2 - 4 months (Sinn et al., 2010), and a longer duration may be more effective in producing longer-term behavioral change. The drink will be administered by the parents to their children at any time each day.

Primary Outcome Measures

The pre-defined primary outcome measures are externalizing behavior problems. Secondary outcomes included internalizing behavior problems and neurocognitive / academic mediators. We include additional *secondary* measures of reactive-proactive aggressive behavior and callous-unemotional traits to replicate the pilot findings and explore antisocial subtypes (the pilot data showed stronger effects for reactive aggression).

Externalizing and internalizing behavior problems in children and caregivers will be assessed using the Multicultural Family Assessment Module (MFAM - Achenbach et al., 2015) which constitutes counterpart scales of the Child Behavior Checklist (CBCL/6-18), Youth Self-Report (YSR), Adult Self-Report (ASR), and Adult Behavior Checklist (ABCL). Reliability, validity, and cross-cultural generalizability have been documented in over 100 societies (Achenbach & Rescorla, 2001; Achenbach & Rescorla, 2001; Rescorla et al., 2012). The Externalizing scale includes Aggressive Behavior and Rule-Breaking Behavior, while the Internalizing scale includes Anxious/Depressed, Withdrawn, and Somatic Complaints. Additional syndromes include Attention Problems, Social Problems, and Thought Problems. Instruments are also scored on DSM-oriented scales comprising items judged by international clinical experts to be very consistent with DSM diagnostic criteria.

Adolescents will rate themselves on the Youth Self-Report YSR. The caregiver will rate their child on the CBCL/6-18, themselves on the ASR, and their spouse on the ABCL. We have established measurement invariance of the CBCL in this cohort in Mauritius (Yarnell et al., 2013). Teacher ratings of the child will be assessed using the Teacher Report Form of the MFAM. In consultation with [name] (Consultant), we will adopt the same system he has used in his national surveys to successfully obtain individual-based teacher ratings using payment to the teacher with a parental permission letter (Achenbach & Rescorla, 2001).

Other measures of antisocial behavior taken in the pilot data will be repeated here to assess replicability of original findings. These include the *Reactive and Proactive Aggression Questionnaire* (RPQ), Developed by the PI, this instrument assesses two overlapping yet distinct forms of aggression (Raine et al., 2006). *Psychopathic-like traits* will be assessed by caregivers using the Antisocial Personality Screening Device (APSD) consisting of three sub-scales: callous-unemotional traits, narcissism, and impulsivity (Frick et al., 2000). Due to the introduction of callous-unemotional traits in DSM as a specifier for conduct disorder, adolescents will also complete the Inventory of Callous-Unemotional Traits (ICU - Essau et al., 2006). In caregivers, psychopathy will be assessed using the self-report *Psychopathic Personality Inventory* (PPI - Lilienfeld & Andrews, 1996). These measures also showed significant changes in the pilot study.

Secondary Outcome Measures

Neurocognitive Risk Factors. These encompass cognition, emotion, and motor functioning and will be assessed using the CANTAB (Robbins et al., 1994). This battery is selected because it is language and culture independent, has been extensively validated on children and adolescents, and its user-friendliness to adolescents helps assure feasible implementation. Measures are selected based on the most pertinent neurocognitive domains relevant to antisocial / aggressive behavior (e.g. Ogilvie et al. 2011; Raine et al., 2005; Cauffman et al., 2005), including attention (Attention Switching Task), cold executive functioning (Stockings of Cambridge), hot executive functioning (Cambridge Gambling Task), emotional decision-making (Affective Go/NoGo), social / emotional cognition (Emotion Recognition Task), and impulse control (Stop Signal Task). Minimal reading (2 tasks) or no reading (4 tasks) is needed.

Academic Skills. As per C2's recommendation for "expanded assessment" to cover other domains, academic skills will be assessed using the Wide Range of Achievement Test (WRAT-4 – Wilkinson & Robertson, 2006) which provides measures of mathematics, spelling, sentence completion, and word reading. Mauritian children today are fluent in English which is the oral and written language of instruction from age 5.

The parent (CBCL) and youth (YSR) reports also include School Competence scales, while the teacher (TRF) form includes Academic Performance and Adaptive Functioning (Achenbach et al., 2015). These will extend the scope on mechanistic processes beyond neurocognitive functioning.

As in the pilot study, parental belief in treatment allocation to the omega-3 group (yes, no) will be measured at the end of treatment to assess influence on behavioral change. Demographics will again be collected on entry into the study, together with an adverse events questionnaire at the end of treatment.

Adherence to protocol and blood assays.

Adherence to the treatment regimen is a frequent problem in RCTs. As before, this will be assessed by assays of omega-3 from finger-prick blood taken from both caregiver and adolescent at all four time-points, with microwave irradiation assays conducted by team member [name] an NIAAA. For full methodological details see Lin, Loewke, Hyun, Leazer, & Hibbeln (2012). In response to C2, blood will additionally be assessed mid-way through supplementation (3 months). To help further enhance adherence, participants will be called every two weeks to remind them to use supplements, and to assess frequency of drink consumption by caregiver and adolescent in that time period (number of drinks / two weeks). To further facilitate compliance, participants will be given a bonus payment if their % blood omega-3 levels have risen higher than the bottom quartile of the population.

Statistical Methods

Overview. An intention-to-treat (ITT) design using all randomly assigned participants will be employed for all data analyses. All data will be blindly double-entered and checked for consistency.

Aims 1 and 2 (Primary Outcome). These hypotheses will be addressed using adolescent and caregiver externalizing responses gathered at baseline and at 6, 12, and 18 month follow-ups. Responses for the adolescent will be analyzed separately from responses for the caregiver. For each separate set of responses, linear mixed effects models (Molenberghs & Verbeke, 2005) will be used to describe both the pattern of response and the within-subject covariance structure across time points. Primary analyses will not include baseline covariates, as the randomization will balance the treatment groups and eliminate selection bias. To enhance power by controlling for variability in response (Kahan et al., 2014), a small set of baseline covariates (e.g. gender, age, ethnicity) will be included in supplementary analyses.

The response may be transformed (e.g. log transformation) to reduce levels of skewness in the response to acceptable levels, as assessed by examination of residuals. Models will include binary indicators for adolescent group (omega-3 vs placebo), caregiver group (omega-3 vs placebo), and time (four level factor for times 0, 6, 12, and 18), and group by time interaction terms, as fixed effects. Time is modeled as a discrete factor to accommodate the patterns observed in our prior study (see Figure under Preliminary Data) where the omega-3 adolescent groups are similar at baseline and 6 months, and separate at 12 months. Covariance structure models (e.g. random effects, autocorrelated residuals) will be compared using information criteria in models containing all main effects and interactions of interest. Once the covariance structure has been chosen, the fixed effects will be assessed for significance using likelihood ratio tests.

Parameter estimates, standard errors, and 95% confidence intervals will be reported. In the case of a multiple degree of freedom test (e.g. group by time interaction, with 3 df), single-df contrasts will be estimated and reported, to explain the nature of the interaction.

For the adolescent, Hypothesis 1a will be addressed using a child group by time interaction term (time trends for omega-3 and placebo group need not be parallel), or a child group main effect if the interaction term is non-significant (parallel time trends). Similar models will address the corresponding Hypothesis 1b for the caregiver responses. For both the adolescent and caregiver responses, Hypothesis 2a will be tested by an adolescent group by caregiver group by time interaction, or by an adolescent by caregiver interaction if the four adolescent by caregiver group trends are parallel.

Aim 3 (Secondary Outcome). Working hypothesis 3a (change in neurocognitive and academic factors) will be tested using the same mixed effects models as outlined above in aims 1 and 2. Working hypothesis 3b (mediation), whether improvement in neurocognitive variables (e.g. impulse control) or academic WRAT scores partly account for the treatment effect on child behavior will be assessed using mediation analyses. Based on the prior study (Raine et al, 2015), effects of supplementation should emerge by the 12-month time point. Analyses will test whether changes in risk factors between baseline and the 6 month point mediate the 12-

month treatment effect. These analyses will be conducted using the PROCESS SPSS macro (Hayes, 2012), which will also be used to assess moderated mediation (e.g. neurocognitive measures mediate outcomes more strongly in younger adolescents). To test significance of the indirect effects (i.e. mediation), bias-corrected confidence intervals for the indirect effects will be generated using 10,000 bootstrap samples. To assess extent of mediation, the reduction in variance explained in treatment outcome by the intervention after controlling for improved parental behavior (the mediator) will be calculated in a two-step regression. Equivalent analyses will be performed for the other neurocognitive variables.

Moderator Analyses. We will conduct exploratory analyses on age, gender, ethnicity, initial general nutritional status, and initial omega-3 levels. To test for moderators, we will extend the models of the primary hypotheses to include main effects for each moderator and their interaction effect with the group factor. Analyses will initially consider each moderator separately, and multivariate models will examine the joint effects of significant moderators. As a secondary analysis we hypothesize that better treatment outcome may be observed in children who start out with lower blood levels of omega-3, and have diets high in omega-6 (which compete with omega-3 for uptake).

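### Do the oldest adolescents outgrow the CBCL/6-18 before month 18 in a way that requires a change to the plan?

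*Combined protocol and SAP*

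**What the plan says.** The section on participants and attrition sets the age limits: "Adolescents will be aged between 11 and 18 years old, willing to participate in an RCT, and residing in the community". None of the four exclusion criteria concerns age during follow-up. The same section describes the source pool: "There are currently 1,126 children aged 11-18 years actively participating in the Mauritius Child Health Project". Of these, 124 took part in the earlier trial and are excluded.

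The Design Overview fixes the visits: "Assessments will take place at 0 months (baseline), 6 months (end of supplementation), 12 months (6 months post-treatment), and 18 months (12 months post-treatment".

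Primary Outcome Measures makes externalizing behavior the primary outcome and assigns the instruments. For the caregiver: "The caregiver will rate their child on the CBCL/6-18, themselves on the ASR, and their spouse on the ABCL". For the adolescent: "Adolescents will rate themselves on the Youth Self-Report YSR". Teachers complete the Teacher Report Form. The document states no age range for the self-report or teacher forms.

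Statistical Methods, Aims 1 and 2, takes all four visits into the mixed models: "These hypotheses will be addressed using adolescent and caregiver externalizing responses gathered at baseline and at 6, 12, and 18 month follow-ups". Under Randomization: "We aim to achieve balanced groups on three main child covariates: age, gender, and ethnicity". Moderator Analyses lists age among the exploratory moderators.

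**The concern.** The upper entry age equals the upper age in the form's name, and follow-up adds a year and a half. The entry limit therefore leaves no room for ageing, and an adolescent who enters near the top is older than 18 at later visits. The plan does not say whether the CBCL/6-18 is still used then, whether an adult form replaces it, or whether the score is set to missing.

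If a form were changed or dropped for the oldest adolescents, one of the three informants on the adolescent primary outcome would lose comparability or data. This would fall mainly at month 18, the visit this trial adds to the pilot design, and at one end of the age range, where a moderator analysis is planned. An unwritten rule could also be settled after data have been seen.

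**Working it through.** **Inputs.** Entry age 11 to 18, 400 adolescents, and a pool of 1,126 − 124 = 1,002 (section on participants). Visits at 0, 6, 12 and 18 months (Design Overview). Form named 6-18 (Primary Outcome Measures). The plan gives no figure of its own on this point to reproduce. Three inputs are assumptions: the age distribution; the meaning of 18 (up to the 18th or the 19th birthday) for entry and for the form; and, for precision, a 200 versus 200 comparison, two-sided 5%, 80% power, and the pilot's 8% attrition carried over.

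**Share out of range.** Let Amax be the upper entry age, L the age at which the form ends, and f the follow-up in years. With uniform ages, p = max(0, (Amax − (L − f)) / (Amax − 11)).

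| Reading | Amax | L | Month 6 | Month 12 | Month 18 |
|---|---|---|---|---|---|
| A | 18 | 19 | 0% | 0% | 0.5/7 = 7.1% (29 of 400) |
| B | 19 | 19 | 6.3% (25) | 12.5% (50) | 1.5/8 = 18.8% (75) |
| C | 18 | 18 | 7.1% (29) | 14.3% (57) | 1.5/7 = 21.4% (86) |
| D | 19 | 18 | 18.8% (75) | 25.0% (100) | 2.5/8 = 31.3% (125) |

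Under D, 1/8 = 12.5% (50) would already be out of range at baseline.

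**Sensitivity to the age distribution.** If the density falls linearly to zero at the top age, the share is p²; if it rises linearly from zero, it is 1 − (1 − p)². At month 18 this gives 0.5% to 14% (A), 3.5% to 34% (B), 5% to 38% (C) and 10% to 53% (D).

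**Precision if every out-of-range month-18 score were lost.** Each arm keeps 200 × 0.92 = 184 before this loss. The standard error grows by 1/√(1 − p), and the smallest detectable d is 2.80 × √(2 / (184 × (1 − p))).

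- No loss: 2.80 × √(2/184) = 0.29.
- A: standard error × 1.04, d = 0.30.
- B: × 1.11, d = 0.32.
- C: × 1.13, d = 0.33.
- D: × 1.21, d = 0.35.

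The most adverse corner is D with a rising age density: 1 − p becomes 0.6875², so d = 0.29/0.6875 = 0.42. All these figures look at month 18 alone and give no credit for the earlier visits that the mixed model retains.

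**Cost of an entry cap.** Keeping everyone in range needs a cap of L − 1.5, that is 17.5 or 16.5 years. The remaining pool is 1,002 × (cap − 11)/(Amax − 11): 930 (A), 814 (B), 787 (C) or 689 (D), before the other exclusions and refusals. Filling 400 places then needs 43%, 49%, 51% or 58% of the pool, against 400/1,002 = 40% now.

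**What the text implies.** The plan names one caregiver form for the child, without exception, and takes responses from all four visits. Read literally, the CBCL/6-18 is used throughout. The adult forms are assigned only to the caregiver's self-rating and to the rating of the spouse. The analysis section provides for transforming a skewed response and mentions neither age norms nor discarding late scores.

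**The case for a change.** The strongest case for a change is that the facts are not in dispute and the omission holds on every reading: even under A, anyone older than 17.5 at entry is past the form's span at month 18. The measurement invariance cited for the CBCL in this cohort is not claimed beyond that span. The related adult forms come with no rule for linking scores, and a switch within one adolescent's series would mix form with time, which the model treats as a discrete factor. The mixed model does not restore lost month-18 data. Loss due to age would also blur the planned check on whether missingness moderates outcome. No informant is named as the primary one, so the caregiver rating cannot be set aside. A one-paragraph rule would cost little.

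The silence of the plan stands, and so does the point about measurement validity past the form's named age. The harm does not follow. Most of these consequences need a switch or a discard that the plan does not prescribe. Keeping the form, which is what the text says, leaves the arms measured alike at each visit. If scores were lost, the cause would be age, which randomization aims to balance, so the cost is precision and coverage rather than a difference built in between arms. The plan expects the effect to have emerged by month 12, and its mediation analysis targets that visit. There the uniform share ranges from 0% (A) to 25% (D).

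**Conclusion.** The gap is real but small, and no change to the plan is called for. Some of the oldest adolescents will be rated past the age in the form's name: about 7% to 31% at month 18 under uniform ages, and 0.5% to 53% across the other age patterns tried. The document cannot narrow this range, because it gives neither the age distribution nor the form's exact limit.

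The consequence is limited to measurement validity, and at most some precision, for one of three informants, mainly at month 18. Under uniform ages, total loss of those scores would move the detectable d from 0.29 to between 0.30 and 0.35. The 0.42 figure needs the least favorable reading, an age distribution piled up at the top, and complete loss, all together.

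An entry cap is a debatable trade: it gives up about 7% to 31% of the pool and part of a planned moderator's range, and its value depends on a form limit that the document does not state. A written rule to keep the same form and scoring would match what the text already implies. An analysis restricted to adolescents in range would change no primary result. Both can be left to the analysts' ordinary judgment. The conclusion rests on the literal reading that the CBCL/6-18 is used at all visits in all arms.

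### The factors used to balance the urn randomisation are left out of the primary models because they are balanced, which gives up modest precision in the between-subject tests

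*Combined protocol and SAP*

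**What the plan says.** All references are to the combined protocol and SAP.

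- **Randomization.** "Participants will be randomized into four groups using urn randomization, a covariate adaptive randomization method". Among the reasons given for this choice is that "it improves power over standard designs". The committed factors all belong to the child: "We aim to achieve balanced groups on three main child covariates: age, gender, and ethnicity". The parents' record of externalizing behavior is mentioned only as something "which we could add as a fourth covariate to further ensure that groups are balanced".
- **Statistical Methods, Aims 1 and 2 (Primary Outcome).** "Primary analyses will not include baseline covariates, as the randomization will balance the treatment groups and eliminate selection bias". The next sentence gives adjustment its own purpose, "To enhance power by controlling for variability in response", but assigns it to a secondary place: "a small set of baseline covariates (e.g. gender, age, ethnicity) will be included in supplementary analyses". Both family members' outcomes are analysed under this heading: "These hypotheses will be addressed using adolescent and caregiver externalizing responses gathered at baseline and at 6, 12, and 18 month follow-ups".
- **Order of testing, same section.** Hypotheses 1a and 1b are tested first by a group-by-time interaction, and by a group main effect if that interaction is not significant. Hypothesis 2a is tested by the three-way interaction with time, or by the adolescent-by-caregiver interaction if the four trends are parallel.

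**The concern.** The two sections use the same balance for opposite ends. The Randomization section chooses covariate-adaptive allocation partly for power. The primary analysis then cites the resulting balance as the reason to ignore the covariates.

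Balance protects against chance differences between arms. It does not remove the variation in outcome that age, gender and ethnicity cause within each arm. A model without these factors leaves that variation in the residual, so the standard error of a between-subject comparison is larger than it need be. Where allocation has also reduced the between-arm part of that variation, the unadjusted standard error slightly overstates the real uncertainty.

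At stake is some power in tests that decide primary hypotheses. The plan recognises this gain but takes it only in a supplementary analysis, and the covariate list there is given by example, so it is not fixed.

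**Working it through.** **Inputs from the documents.** 400 pairs, 100 per cell (Participants section), so each factorial main effect compares 200 with 200. Gender and ethnicity mix: 51.2% female; 73.2% Indian, 24.5% Creole, 2.3% other. Confidence level 95%.

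**Inputs assumed.** The documents give no alpha, effect size, variance explained or urn parameters. Assumed here: two-sided alpha 0.05; a true main effect of 0.28 SD, which is the difference that 200 v 200 detects with about 80% power; and R2, the share of between-subject outcome variance explained by the three factors, at 5%, 10% or 20%. The plan has no power calculation to reproduce.

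**Step 1. Standard errors (SD units).**
- Main effect, unadjusted: sqrt(2/200) = 0.100.
- Main effect, adjusted: 0.100 × sqrt(1 − R2) = 0.097, 0.095, 0.089.
- Adolescent-by-caregiver interaction over four cells of 100, unadjusted: sqrt(4/100) = 0.200.
- The same interaction, adjusted: 0.195, 0.190, 0.179. The proportional gain is the same, on a test that starts with half the precision.

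**Step 2. How much imbalance the urn removes.** Let f be the variance of the factors' chance imbalance under the urn, relative to simple randomisation. A simulation of 6,000 trials (400 pairs, four arms, one urn per factor level, two age bands, one ball of each other type added after each draw) gave f = 0.775. This assumed urn removes only about 22% of the chance-imbalance variance.

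**Step 3. Power and actual false-positive rate of a main-effect test.**
- Unadjusted power = Phi[(0.28 − 1.96 × 0.1) / (0.1 × sqrt(1 − R2 + f × R2))].
- Adjusted power = Phi[0.28 / (0.1 × sqrt(1 − R2)) − 1.96].
- Unadjusted false-positive rate = 2 × (1 − Phi[1.96 / sqrt(1 − R2 + f × R2)]).
- Number per factor level for 80% power with adjustment = 2 × (1.96 + 0.8416)² × (1 − R2) / 0.28², rounded up. It is 201 without adjustment (R2 = 0).

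| R2 (assumed) | Power, unadjusted | Power, adjusted | False-positive rate, unadjusted | Number per level, adjusted |
|---|---|---|---|---|
| 5% | 80.1% | 81.9% | 4.9% | 191 |
| 10% | 80.2% | 83.9% | 4.7% | 181 |
| 20% | 80.5% | 87.9% | 4.5% | 161 |

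Worked line for R2 = 10%. Unadjusted: 1 − 0.10 + 0.0775 = 0.9775, and 0.084 / (0.1 × 0.9887) = 0.850, giving 80.2%. Adjusted: 0.28 / 0.0949 − 1.96 = 0.99, giving 83.9%.

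**Step 4. The first-line group-by-time test.** Assume equal correlation of 0.6 between visits, complete data, no effect at 0 and 6 months, and 0.28 SD at 12 and 18 months. The within-person variance is 0.4, so the variance of a group difference at one visit, within person, is 0.4 × 2/200 = 0.004. The effects' squared deviations from their mean sum to 4 × 0.14² = 0.0784. The noncentrality is 0.0784 / 0.004 = 19.6 on 3 df, which gives about 97% power. Covariate effects that are constant over time do not enter this calculation. A simulation of the same set-up with simple allocation, adding covariate-by-time terms to the adjusted model, agreed: unadjusted v adjusted power was 96.8% v 96.7%, 97.0% v 96.7% and 96.9% v 96.5% at R2 of 5%, 10% and 20%.

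**The case against.** The strongest reply is that the figures in Step 3 describe a fallback. The first test of each primary hypothesis is an interaction with time, the baseline response is already in the model, and within-person contrasts cancel any covariate effect that is constant over time. This stands. A reader might infer that the whole primary result is less precise than it should be; Step 4 shows that this does not follow. The point is confined to the between-subject tests, which remain named routes for the primary hypotheses.

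Second, the plan already includes an adjusted analysis. That also stands: the dispute is which of two valid models is primary. It does not rescue the stated reason for the choice.

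Third, R2 is unknown. At 5% the gain is about 2 points of power, and nothing in the documents suggests that a child's age and gender explain much of an adult's behavior. This is accepted as a limit on size.

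Two further readings are tempting and are not supported:

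- **That the omission biases the result or gives markedly wrong error rates.** Under the assumed urn the false-positive rate stays between 4.9% and 4.5%. A rate as low as 2.8% at R2 = 20% needs perfect balance, which the protocol does not propose.
- **That the caregiver comparison is flawed because no caregiver factor is firmly in the urn.** Randomisation is valid without one, and baseline caregiver externalizing is in the mixed model. A life-course record would also need a chosen measure, cut-points and a missing-data rule before it could define an urn. Adding it is a design preference.

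**Conclusion.** The concern holds as a modest loss of efficiency with an inconsistent rationale. The unadjusted primary test is valid, unbiased and very slightly conservative. For the between-subject main effects, adjustment would raise power from about 80% to 82%, 84% or 88%; at R2 = 10% this is equivalent to about 20 more pairs per factor level (201 − 181). These figures rest on the assumed alpha, effect size, R2 and urn rule. The group-by-time tests gain little or nothing unless the effects of age, gender or ethnicity change over time, and the caregiver outcome may gain less than the adolescent one. The change is worth making because it costs almost nothing and makes the analysis follow the randomisation. No change to the urn factors is called for.

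**What to change.** In Statistical Methods, Aims 1 and 2, replace the sentence that excludes baseline covariates with wording such as: *The primary mixed models for adolescent and caregiver outcomes will include, as fixed effects, every factor used in the urn randomisation (child age, gender and ethnicity, and any further factor actually used). The model without these factors will be reported as a supplementary analysis.*

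State the coding of age and ethnicity before unblinding. The smallest ethnic category would hold about 9 of 400 pairs (0.023 × 400), so a rule for grouping it is needed. If the parents' externalizing record is used in the urn after all, the same sentence carries it into the models; its use need not be required.

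**Cost.** The factors have to be known at allocation and an adjusted model is already planned, so no new data are needed. With age as a linear term, gender as one term and ethnicity as two, about 4 degrees of freedom out of about 400 are spent. Covariate-by-time terms are not needed for this fix; each would cost 3 more.
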